8.2 Statistical Methods

Primary analysis plan:

To test whether OH correlates with the nonmotor symptoms of fatigue, anxiety, depression, apathy, and cognitive impairment, we will compare these variables between the PD (+OH) group to the PD (-OH) group using the Mann-Whitney *U* test. Although this pilot study is likely underpowered for additional analyses, we will then construct several linear regression models with each nonmotor variable as an outcome, and also include important clinical (e.g. disease duration, total LDED) and demographic variables in the models in order to test if OH is independently associated with these nonmotor outcomes.

Secondary analysis plan:

To test whether central NA dysfunction is involved in these nonmotor symptoms, we will correlate each variable (i.e. quantified scores of depression, apathy, anxiety, fatigue, and cognition) with the difference before and after yohimbine in the change in catecholamine and AVP levels supine and at 60 degree tilt. We will also correlate the nonmotor scores with pupillary redilation speed, which measures sympathetic function, before and after yohimbine. We will compare change in anxiety, mood, and fatigue scores (measured on a visual analogue scale) before and after yohimbine between the PD (OH+) and PD (OH-) groups using the Mann-Whitney *U* test. We will also compare the changes in BP parameters before and after yohimbine between groups.

After these initial correlations and comparisons, we will construct linear regression models incorporating clinical and demographic variables of interest in order to test if our measures of NA dysfunction independently predict the nonmotor symptoms of PD, though we expect these analyses to be underpowered. Finally, we will test if central NA dysfunction (measured through changes in catecholamines and pupillary response to yohimbine, as above) explains the relationship between OH and the nonmotor symptoms of PD by incorporating our measures of central NA dysfunction into the linear regression models described above, and testing whether the relationship between OH and nonmotor symptoms persist.

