3.1 General Design

This is a cross-sectional pilot study comparing 11 PD patients with OH to 11 PD patients without OH. OH will be defined as a drop in systolic BP of ≥ 20 mmHg or diastolic BP ≥ 10 mmHg within 5 minutes of standing (measured at 1, 2, and 5 minutes).^{59, 67} The study will include two clinical visits and a follow-up phone call 24-72 hours after the 2nd visit. Visits will last approximately 4-5 hours each. After consent has been signed, data from prior neurological exams, such as the H&Y staging, orthostatic vital signs (OVS) and UPDRS scores will be collected from a subject's medical record as part of study data.

For visit 1, subjects will be required to hold levodopa and other dopaminergic PD drugs on the morning of the visit, and other adrenergic medications for at least three half-lives. Subjects will bring their AM dopaminergic doses to be taken at the visit at the direction of study staff in order to coincide with the timing of procedures. Visit 1 will consist of reviewing informed consent and inclusion/exclusion criteria. The PI will confirm eligibility, (women of childbearing potential will undergo a serum pregnancy test as part of this eligibility review). Demographics, medical history, history and current use of alcohol, current and prior smoking status, and concomitant medications will be recorded. HR and BP response to deep breathing (DB) and Valsalva maneuvers, and vibrotactile detection thresholds, will also be tested. The subject will also undergo neurocognitive testing and neuropsychiatric assessments. OVS will be taken before administration of the subject's dopaminergic medications, and at approximately 30 minutes and 1 hour after dopamine administration. Dynamic pupillometry will be evaluated before and approximately 1 hour after administration of the subject's dopaminergic medications. If the subject has not had a CBC and CMP in the past 6 months, the PI will order and review these blood levels for any clinically significant abnormalities. This visit will last approximately 4-5 hours.

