8.1 Sample Size Determination

Our primary study objective is to compare the nonmotor symptoms of fatigue, anxiety, depression, apathy, and cognitive impairment between the OH and non-OH groups. If we aim to detect a clinically significant difference of 2 points on an 11 point visual analogue fatigue scale, only 4 patients in each group are needed, using a 1-way test of means and assuming a population standard deviation of 1, $\alpha = 0.05$ and $\beta=0.80$. However, it is important to recognize that this is an investigative pilot study; since little research has been done in this area and we cannot be certain

of these assumptions, it is entirely possible the study will be underpowered for at least some of our primary and secondary outcomes.

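### The correlations meant to show noradrenergic involvement in symptoms appear to pool OH and non-OH patients, so on their own they cannot show a link beyond OH status

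*Protocol*

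**What the plan says.** Section 3.1 fixes the sample by OH status: "This is a cross-sectional pilot study comparing 11 PD patients with OH to 11 PD patients without OH".

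Section 8.2, secondary plan, states an aim and a method together: "To test whether central NA dysfunction is involved in these nonmotor symptoms, we will correlate each variable". The variables are the depression, apathy, anxiety, fatigue and cognition scores. Each is set against the yohimbine-induced difference in the catecholamine and AVP changes, and then against pupillary redilation speed. No coefficient, stratification or OH adjustment is named for these correlations. The visual analogue and blood pressure comparisons in the same paragraph are explicitly between OH groups.

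Two regression steps follow. The first asks whether the noradrenergic (NA) measures independently predict symptoms, adjusting for clinical and demographic variables; OH is not named. The second adds the NA measures to the models that already hold OH, and asks whether the OH association remains.

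The protocol looks for an OH group difference on both sides of the correlation: in symptoms (section 3.2, primary) and in catecholamine, AVP and pupillary responses (section 3.3, secondary).

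**The concern.** When a sample is built from two selected groups and both variables differ between them, the group difference alone produces a correlation. The correlation then partly restates two comparisons that are already planned.

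This matters because section 1.1 sets out three rival explanations of the OH–symptom link (disease progression, neurochemical, causal), says that treatment would differ between them, and says that earlier studies have not separated them. Under disease progression, the areas behind OH and the areas behind symptoms fail together. A pooled correlation could then arise with no direct link between NA function and symptoms. The same section says that the results may lead directly to treatment trials aimed at the NA system.

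The later models do not clearly close the gap. The first does not name OH as a covariate. The second holds OH and the NA measures together, but its stated test is on the OH term. Nowhere is a conclusion about the NA measure tied to its coefficient given OH.

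**Working it through.** **The plan's own figure.** The protocol gives no figure for the correlations. Its only calculation is in section 8.1: "only 4 patients in each group are needed" for a "difference of 2 points on an 11 point visual analogue fatigue scale", "assuming a population standard deviation of 1". With 5% alpha and 80% power (the 0.80 is labelled beta but can only be power), the normal approximation gives

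n per group = 2 × (1.960 + 0.842)² × 1² / 2² = 3.9, so 4 (two-sided)

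n per group = 2 × (1.645 + 0.842)² × 1² / 2² = 3.1, so 4 (one-sided)

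The figure reproduces. It bears on this point only because 2 points with SD 1 is a 2 SD difference in fatigue, which marks the upper end of the range below for one variable. It is a difference to detect, not a difference the protocol reports.

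**Inputs.** 11 and 11 patients (section 3.1). Zero correlation inside each group. Group differences d1 (symptom) and d2 (yohimbine response), in within-group SDs. The documents give neither, so 0 to 2 SD is an assumption.

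**Formula.** In a 50:50 mixture the between-group covariance is d1·d2/4 and each variance is 1 + d²/4, so

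pooled r = (d1·d2/4) / √[(1 + d1²/4)(1 + d2²/4)]

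For d1 = d2 = 1: 0.25/1.25 = 0.20. For d1 = d2 = 2: 1/2 = 0.50.

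**Rejection rates.** Simulated trials with normal data, two-sided 5% level:

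| d1 / d2 (SD) | expected pooled r | pooled Spearman | given OH |
|---|---|---|---|
| 0 / 1 | 0.00 | 5% | 5% |
| 0 / 2 | 0.00 | 5% | 5% |
| 0.5 / 0.5 | 0.06 | 6% | 5% |
| 0.8 / 0.8 | 0.14 | 9–10% | 5% |
| 1.0 / 1.0 | 0.20 | 15% | 5% |
| 1.3 / 1.3 | 0.30 | 29% | 5% |
| 1 / 2 | 0.32 | 33% | 5% |
| 2.0 / 2.0 | 0.50 | 79% | 5% |

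Both variables must differ for any inflation to appear, and it is small below about 0.8 SD.

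**Cost of adjusting when the groups do not differ.** With a true within-group correlation of 0.5, power (Pearson) is 68% pooled (20 degrees of freedom) and 66% given OH (19 degrees of freedom).

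**Cost when NA loss also causes OH.** Assumptions, none from the documents: OH is the top 30% of a liability correlated 0.8 or 0.9 with NA loss; NA loss correlates 0.5 or 0.6 with the symptom; the NA measure has reliability 0.7 or 1.0; 11 patients are drawn from each side. Over the eight combinations (10,000 trials each), the pooled Spearman test detects the link in about 48% to 84% of trials and the partial test given OH in about 19% to 59%. The loss is 24 to 39 percentage points. For example, with 0.9, 0.6 and 0.7 the figures are 67% and 28%.

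**The case against.** The strongest reply has four parts.

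- *Pooling is not written down.* This is correct. A reader might infer that the protocol prescribes a pooled correlation; it leaves the grouping unstated. Pooling is the natural reading because the neighbouring comparisons are explicitly by group, and a separate analysis plan could say otherwise.
- *The plan goes further than these correlations.* It calls them initial and follows them with regressions. OH could count as a clinical variable in the first set, and the last set holds OH and the NA measures together, so the NA coefficient given OH will be available. This stands, and it makes the remedy cheap. What remains is that the stated test there is on the OH term.
- *A significant pooled correlation need not be false.* A reader might infer that it would be. The documents do not support that. Under the neurochemical hypothesis in section 1.1, NA loss underlies both OH and symptoms, and the between-group part is then genuine signal. The zero-within-group case above means no association given OH, not no association at all.
- *Making the within-group result decisive would be wrong in the other direction.* This also stands. The power loss above shows why, and disease progression could link NA loss and symptoms inside each OH group as well, so adjustment does not by itself separate the hypotheses.

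These are also secondary analyses in a pilot that says its regressions are likely to be underpowered.

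**Conclusion.** The point holds in a limited form. On the natural reading, the analysis named as the test of NA involvement cannot show a link between NA function and symptoms beyond OH status. The rejection rate with no within-group association runs from 5% (only one variable differs) through about 15% (1 SD in both) to about 79% (2 SD in both). Those sizes are assumptions, as are normal data and equal within-group SDs.

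Two stronger conclusions are not supported: that the plan would produce a false claim, and that only the within-group result should count. The pooled value mixes two sources that it cannot tell apart; the adjusted value removes one of them, at a real cost in power if NA loss also causes OH. For an exploratory secondary analysis this is a worthwhile, inexpensive improvement and not a flaw that undermines the trial.

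**What to change.** In section 8.2:

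1. State whether the correlations use all 22 patients. Beside each pooled correlation, report the partial Spearman correlation given OH group, with a plot that shows the two groups separately.
2. In the final models that already hold OH and the NA measures, report the NA coefficient with its confidence interval as well as the OH term.
3. Add a rule of interpretation: NA involvement independent of OH is not claimed from the pooled value alone, and a null adjusted result is not read as absence of involvement.

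The data are already collected, so the work is one extra line per correlation. The statistical cost is one degree of freedom, plus clearly lower power for the adjusted estimate if NA loss also causes OH. That is why both are shown and neither is made solely decisive.

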1.1 Background

Although Parkinson's disease (PD) is traditionally considered a movement disorder resulting from dopamine deficiency, there is increasing recognition that nonmotor symptoms are prevalent and drastically impact quality of life.¹⁻³ Orthostatic hypotension (OH) and symptoms of fatigue, depression, apathy, anxiety, and cognitive impairment (neuropsychiatric (NP) symptoms) are among the most bothersome symptoms in PD, and can occur early in the disease course.^{1,3,4} OH in PD is due to a combination of cardiac sympathetic denervation, peripheral vascular sympathetic denervation, and baroreflex failure.⁵⁻⁷ Involvement of central nervous system (CNS) areas that mediate autonomic nervous system (ANS) function, such as the anterior cingulate and insular cortex, have also been radiologically and pathologically associated with OH in patients with PD.^{8,9} Importantly, OH has been associated with depression, dementia, and poor prognosis in PD^{5, 10-13}, though not all studies agree¹⁴ - likely due to methodological differences.⁵

The reasons for the association between OH and NP symptoms remains unknown.⁵ A disease progression hypothesis suggests that as α -synuclein inclusions spread, brain areas that mediate OH and NP symptoms degenerate simultaneously.^{15,16} A neurochemical hypothesis suggests that since noradrenergic (NA) neurons are selectively damaged in PD, peripheral sympathetic degeneration is accompanied by degeneration of CNS NA areas such as the locus coeruleus (LC), which has been implicated in human cognition and arousal.¹⁷⁻¹⁹ A third hypothesis is that OH itself leads to cognitive decline, since both OH-induced cerebral hypoperfusion and OH-associated supine hypertension can cause vascular brain injury,^{20,21} though at least one study refutes this theory.²² Determining reasons for the association between OH and NP symptoms is critical since treatment will differ significantly: the neurochemical explanation suggests that norepinephrine (NE) replacement should treat OH simultaneously with NP symptoms, while the causal explanation suggests that treating OH will then lead to better cognition and mood. In addition, understanding the association between OH, NP symptoms, and NA dysfunction may help improve prognostication for patients with PD, and may help to identify a PD subgroup with distinct pathophysiology that requires a different treatment approach.¹³ Unfortunately, studies to-date have not distinguished between these hypotheses.

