In this study, we propose to test if NA dysfunction is associated with depression, cognition, apathy, anxiety, and fatigue in PD. First, we will test if OH in patients with PD is associated with other aspects of NP in which the adrenergic system plays a prominent role: fatigue/arousal,

attention/cognition, and apathy/depression. We will then conduct a series of physiologic tests to elucidate the contributions of central and peripheral NA dysfunction in OH in PD, and use these results to see if NA dysfunction mediates any associations between OH and NP symptoms.

These interrelated aims will help to determine if central NA dysfunction is associated with OH in PD, and whether NA dysfunction is associated with the NP symptoms in PD. These results may lead directly to treatment trials that target the NA system with the potential to significantly improve the lives of PD patients with bothersome nonmotor symptoms.

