For Visit 2, subjects will again be required to hold levodopa and other medications that may interfere with autonomic testing. Women of childbearing potential will have a urine pregnancy test performed prior to the HUT. An IV will be placed as per HUT procedure. HUT testing will be conducted twice, once prior to and once after yohimbine administration. The subjects will complete visual analogue scales measuring anxiety, mood, and fatigue prior to and after yohimbine administration. Dynamic pupillometry will also be evaluated prior to yohimbine administration and after yohimbine administration. Serum arginine vasopressin (AVP) and norepinephrine (NE) will be drawn twice prior to yohimbine administration and twice after yohimbine administration. One draw will be in the supine position, and the other will be during the head up tilt as outlined below, and then these two draws will be repeated after yohimbine (see Section 7.3, Figure 2).

A follow up study phone call will be made by the study coordinator 24-72 hours after study visit 2. Any adverse events which may have occurred since the study visit will be captured on the subject's AE log.

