3.3 Secondary Study Endpoints

Secondary study endpoints will be:

- Difference between OH and non-OH group in change in supine and orthostatic catecholamine and AVP levels before and after yohimbine administration
- Difference between OH and non-OH group in change in time to pupillary redilation before and after yohimbine
- Change in self-reported anxiety, mood and fatigue before and after yohimbine
- Between group difference in baseline BP rise with yohimbine administration
- Difference in time to recovery of BP after 60 degree HUT before and after yohimbine administration
- Correlation between sympathetic function (measured with pupillary redilation and beat-to-beat BP) and levodopa use

4 Subject Selection and Withdrawal

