4.4.2 Data Collection and Follow-up for Withdrawn Subjects

All study procedures will be discontinued for the subject at the point of being classified as “Withdrawn.” Data collected up to the point of subject withdrawal may be used for analysis. If a patient is terminated early from the study as a result of an adverse event related to study procedures, every effort will be made to follow the patient until the adverse event resolves.

5 Study Drug

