8.3 Subject Population(s) for Analysis

All subjects who complete at least one study visit will be subjected to the study analysis.

9 Safety and Adverse Events

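### Protocol 8.2: loss of significance for OH after adding noradrenergic measures would not show that they explain its link with symptoms

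*Protocol*

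**What the plan says.** The mediation aim is in Protocol 1.1: the physiologic tests are meant to "use these results to see if NA dysfunction mediates any associations between OH and NP symptoms". Section 8.2 answers it in the final step of the secondary analysis plan. The catecholamine and pupillary responses to yohimbine are put "into the linear regression models described above, and testing whether the relationship between OH and nonmotor symptoms persist". The section names no threshold, no change in the OH coefficient, no indirect effect and no interval, and it does not fix how many NA terms or covariates enter.

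Two other planned analyses bear on this step. Section 3.3 lists as a secondary endpoint the "Difference between OH and non-OH group in change in supine and orthostatic catecholamine and AVP levels before and after yohimbine administration". Section 8.2 also fits regressions with clinical and demographic variables "in order to test if our measures of NA dysfunction independently predict the nonmotor symptoms of PD", and expects them to be underpowered. It does not say whether those regressions include OH, or whether either analysis must succeed before the final step is interpreted.

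On the data, symptoms and cognition are scored at Visit 1 (sections 7.1 and 7.2). The yohimbine-response measures exist only at Visit 2: "Serum arginine vasopressin (AVP) and norepinephrine (NE) will be drawn twice prior to yohimbine administration and twice after yohimbine administration" (section 3.1). Section 8.3 states "All subjects who complete at least one study visit will be subjected to the study analysis", and section 4.4.2 adds "Data collected up to the point of subject withdrawal may be used for analysis".

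**The concern.** A coefficient can stop being significant because it shrinks or because it is estimated less precisely. Only shrinkage bears on mediation. Adding variables that are correlated with OH widens the standard error of the OH coefficient even when those variables have no effect on symptoms. The neurochemical hypothesis in section 1.1 expects that correlation, because it has peripheral and central NA degeneration occurring together. With 22 patients there is little precision to spare.

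The direction of the error matters. The caveats in sections 8.1 and 8.2 about low power warn of missed effects. Under the significance reading of this step, low power produces the positive claim that NA dysfunction explains the association, so those caveats give no protection. Section 1.1 says the results may lead directly to treatment trials targeting the NA system.

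A smaller issue is that the models before and after adjustment may be fitted in different patients if some have Visit 1 only. OH could then lose significance through lost observations alone.

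**Working it through.** **1. The plan's own figure.** Section 8.1 uses a difference of 2, SD 1, alpha 0.05 and power 0.80 (printed as β). Per group, n = 2(1.960 + 0.842)²/2² = 3.93, so 4, as stated. This concerns an unadjusted comparison of two means and says nothing about the adjusted models. It does supply the only effect size in the document, d = 2 SD.

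**2. Loss of precision by formula.** With equal groups, Var(b_OH) = σ²/[(n/4)(1 − R²)], where n = 22 and R² is the share of OH variance explained by the added NA measures. The noncentrality is d·√[5.5(1 − R²)]. Take d = 1.25 (a t test at 11 per group then has 80% power), two covariates (assumed) and an unchanged true OH effect:

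| Added NA terms | R² | Noncentrality | df | Power for OH |
|---|---|---|---|---|
| none | 0 | 2.93 | 18 | 0.79 |
| one | 0 | 2.93 | 17 | 0.79 |
| one | 0.25 | 2.54 | 17 | 0.67 |
| one | 0.50 | 2.07 | 17 | 0.50 |

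The correlation with OH does the damage. The lost degree of freedom costs almost nothing.

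**3. Linking R² to a group difference.** For one measure differing by δ within-group SDs, R² = (δ²/4)/(1 + δ²/4). This gives 0.06 at δ = 0.5, 0.20 at δ = 1 and 0.36 at δ = 1.5. The R² values of 0.25 and 0.50 in step 2 correspond to δ of 1.15 and 2.0, so they sit at the strong end.

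**4. Simulation with no mediation.** Settings: 20,000 trials per cell; 11 versus 11; symptom = d·OH + N(0,1); each NA measure = δ·OH + N(0,1) with no effect on the symptom; three noise covariates; least squares; alpha 0.05. The values of δ, the 1.3 SD effect, the number of covariates and the number of NA terms are assumptions. Entries are the percentage falsely *explained* among trials where OH was significant beforehand (75% of trials at d = 1.3, 98% at d = 2). Each triple is one NA measure / three correlated 0.6 / three independent.

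| Rule | δ | d = 1.3 | d = 2 |
|---|---|---|---|
| OH loses significance, used alone | 0.5 | 9.7 / 20.9 / 24.6 | 2.1 / 6.0 / 9.1 |
| same | 1 | 20.7 / 31.8 / 44.9 | 5.6 / 12.7 / 22.2 |
| Plus significant OH–NA difference and NA–symptom regression without OH | 0.5 | 1.9 / 5.5 / 6.8 | 0.6 / 2.4 / 3.6 |
| same | 1 | 8.3 / 17.3 / 25.7 | 3.4 / 9.1 / 16.6 |
| same | 1.5 | 18.2 / 32.7 / 47.8 | 9.1 / 19.2 / 35.9 |
| As above, but NA–symptom regression includes OH | 1 | 1.1 / 3.0 / 3.7 | 0.4 / 1.7 / 2.1 |
| OH coefficient at least halves, instead of a significance test | 1 | 1.4 / 3.9 / 7.9 | 0.5 / 1.7 / 3.9 |

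At δ = 1 the median change in the OH coefficient is 0.00, while its standard error rises by 14 / 26 / 45%. The large-sample value for one measure is √1.25 = 1.12, a 12% rise; chance correlations in 22 patients add to it.

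**5. Different patients.** One NA measure, with 0, 2 or 4 of 22 patients (assumed) lacking Visit 2:

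| Rule | d | δ | 0 missing | 2 missing | 4 missing |
|---|---|---|---|---|---|
| OH loses significance, used alone | 1.3 | 0.5 | 9.7% | 18.3% | 27.6% |
| same | 1.3 | 1 | 20.7% | 27.7% | 36.6% |
| same | 2 | 1 | 5.6% | 9.2% | 14.2% |
| Plus significant OH–NA difference and NA–symptom regression without OH | 1.3 | 1 | 8.3% | 8.1% | 8.3% |
| same | 2 | 1 | 3.4% | 4.2% | 5.3% |

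**6. The proposed replacement.** Percentile bootstrap 95% interval for the OH-adjusted indirect effect, with one measure, two covariates, 1,000 trials and 1,000 resamples stratified by OH (Monte Carlo error about 3 points). False positives at d = 1.3 are 0.5, 0.7, 3.8 and 4.6% at δ = 0, 0.5, 1 and 1.5; at d = 2 and δ = 1 the figure is 1.4%. Power is 18% (δ = 0.5, NA–symptom slope 0.8), 24% (1, 0.5), 44% (1, 0.8) and 73% (1.5, 0.8).

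**The case against.** The protocol gives no p-value rule. If *persist* is judged by the size of the coefficient, the problem mostly goes: with one NA measure, at least halving occurs in 0.5–1.4% of null trials at δ = 1. Nor does the step stand alone. Readers would also see the group comparisons of NA responses and the NA–symptom regressions. With both required, one measure gives 0.6–8.3% at δ of 0.5 to 1. If those regressions include OH, which the aim of independent prediction permits, the rate at δ = 1 is 1.1% or 0.4%. That is below the bootstrap's 3.8% and 1.4%, so on that reading the replacement lowers no error rate. The comparison is also not quite like for like: three covariates for the plan's rule, two for the bootstrap. The document gives no Visit 2 loss, and missing visits add little once the other analyses are required. The analysis is secondary, in a pilot that admits low power.

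Most of this stands as a limit on size. It does not remove the point. The rule is written in the protocol, and its reference to testing makes the significance reading the natural one. No gate is stated. Whether the NA regressions adjust for OH is left open, and that choice moves the one-measure rate from 8.3% to 1.1% at d = 1.3 and δ = 1. If they do not adjust, a marker that merely tracks OH will appear to predict symptoms.

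**Conclusion.** The concern holds, conditional on *persist* being read as a significance test. On that reading the final step of section 8.2 can credit NA dysfunction with explaining the OH association when only precision has been lost. With one NA measure, a 1 SD OH–NA difference and no mediation, the false rate is 6–21% if the step is used alone, 3–8% if the other planned NA analyses must also be significant, and about 1% or less if those analyses adjust for OH. Several NA measures or a stronger OH–NA correlation raise it. Within each range the lower figure is for the 2 SD effect of section 8.1 and the higher for an assumed 1.3 SD. None of the other inputs is in the protocol. Unequal patient sets are a secondary issue, material mainly when the step is used alone. The consequence is confined to an exploratory mediation claim; the Mann-Whitney primary comparison is untouched. The change is worth making because this is the step that answers the mediation aim and its error runs towards a positive answer.

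**What to change.** Amend the last step of the secondary plan in section 8.2 as follows:

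- State that loss of significance of OH after adding NA measures will not be read as mediation.
- Name one NA measure in advance for this step, keep covariates few, and treat the other NA measures as descriptive.
- Fit the models with and without that measure in the same patients, those with Visit 2 data, and report the OH coefficient with its 95% interval from both.
- Base any mediation statement on the OH-adjusted indirect effect (OH to NA measure, times NA measure to symptom given OH) with a bootstrap 95% interval, labelled exploratory.

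The cost is a few sentences and a few lines of code, with no new data. Patients seen only at Visit 1 drop out of this one comparison. Power is low to moderate, 18–73% in the cases examined, so the result is an exploratory estimate and not a confirmatory test. If only one sentence can be added, the first item is the one that matters.
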